- 1040 • One distinct severe hypoglycemia event as defined in section 11.1.2.1

1041 **11.4.2 Criteria for Suspending or Stopping Overall Study**

1042 In the case of an unanticipated system malfunction resulting in a severe hypoglycemia or severe
1043 hyperglycemia event (as defined in section 11.1.2.2), use of the study device system will be
1044 suspended while the problem is diagnosed.

1045 If more than 1 serious hypoglycemia or more than 1 DKA event occurs, the study may be paused
1046 to determine a root cause prior to continuation of the study.

1047 In addition, study activities could be similarly suspended if the manufacturer of any constituent
1048 study device requires stoppage of device use for safety reasons (e.g. product recall). The affected
1049 study activities may resume if the underlying problem can be corrected by a protocol or system
1050 modification that will not invalidate the results obtained prior to suspension. The study Medical
1051 Monitor will review all adverse events and adverse device events that are reported during the study
1052 and will review compiled safety data at periodic intervals (generally timed to the review of
1053 compiled safety data by the DSMB). The Medical Monitor may request suspension of study
1054 activities or stoppage of the study if deemed necessary based on the totality of safety data available.

1055 **11.5 Independent Safety Oversight**

1056 A Medical Monitor will review all DKA and severe hypoglycemia irrespective of relatedness to
1057 study device use, and all serious events (including UADEs) related to study device use at the time
1058 of occurrence. The Medical Monitor also will be informed of any ADEs not meeting criteria for a
1059 UADE.

1060 **Chapter 12: MISCELLANEOUS CONSIDERATIONS**

1061 **12.1 Prohibited Medications, Treatments, and Procedures**

1062 Child participants using glulisine at the time of enrollment will be asked to contact their personal
1063 physician to change their prescribed personal insulin to lispro or aspart for the duration of the trial.

1064 The study devices (study insulin pump, study CGM) must be removed before Magnetic Resonance
1065 Imaging (MRI), Computed Tomography (CT) or diathermy treatment. Participants may continue
1066 in the trial after temporarily discontinuing use if requiring one of the treatments above.

1067 **12.2 Participant Withdrawal**

1068 Participation in the study is voluntary, and a participant may withdraw at any time. For participants
1069 who withdraw, their data will be used up until the time of withdrawal.

1070 **12.3 Confidentiality**

1071 For security and confidentiality purposes, subjects will be assigned an identifier that will be used
1072 instead of their name. Protected health information gathered for this study may be shared with the
1073 third party collaborators. De-identified subject information may also be provided to collaborators
1074 involved in the study after the appropriate research agreement has been executed.

1075 **Chapter 13: STATISTICAL CONSIDERATION**

1076 **13.1 Statistical and Analytical Plans**

1077 This trial is single-armed and not powered to detect differences between groups. The study is
1078 designed to obtain a primary safety profile on patients in this age-group.

1079 This study is an early feasibility study that will test the safety of t:slim X2 with Control-IQ
1080 Technology in an outpatient setting. These studies would generate up to 75 days of closed-loop
1081 data. This sample size allows for subject withdrawal.

1082 **13.2 Statistical Hypotheses**

1083 **13.2.1 Primary Outcome**

1084 Number of subject with less than 6% time below 70mg/dL and less than 40% time above
1085 180mg/dL.

1086 **13.2.2 Secondary Outcome**

- 1087 1. % time spent <70 mg/dl, <60mg/dl, <54mg/dL, and <50mg/dL
- 1088 2. % time spent >180mg/dl, and >250mg/dl, >300 mg/dl
- 1089 3. % time spent between 70-180mg/dl
- 1090 4. % time spent between 70-150mg/dl
- 1091 5. Number of hypoglycemia below 70 mg/dL
- 1092 6. Number of carbohydrate treatments, as well as total amount of carbohydrates used for
1093 treatments.
- 1094 7. Time spent in closed loop
- 1095 8. Time with available CGM
- 1096 9. Number of subject with more than 70% time in 70-180mg/dL range with less than 4%
1097 time below 70mg/dL

1098 **13.2.3 Success Criteria / Goal**

1099 As a general rule, a session will be considered useful for data analysis if the subject completes
1100 close to 80% of the active study protocol. Sessions are considered separate: (i) Supervised
1101 Phase=complete at least 38 hours of AP; (ii) at home use=complete at least 56 hours of AP.

1102 *The primary goal will be considered met if the primary outcome is achieved for 65% or more of
1103 the subjects.*

1104 **13.2.4 Statistical Analysis Plan**

1105 Proportions of subject matching primary criteria will be computed and directly compared to 65%
1106 (considered baseline). Further analysis will be performed using a chi² test of goodness of fit. Based
1107 on prior data in 6-12 year olds we anticipate a possible effect size of 0.64, which would allow to
1108 detect a difference with 70% power considering our sample size.

CLINICAL PROTOCOL

1109 Overall outcomes will be compared to the normative data below (values derived from the analysis
1110 of 30 6-12 year old T1D subjects using pumps and CGM and rounded for ease of use):

	Baseline	
	mean	std
% time below 50mg/dL	0.5%	0.5%
% time below 54mg/dL	1%	0.8%
% time below 60mg/dL	2%	1%
% time below 70 mg/dL	4%	2.5%
% time between 70-140mg/dL	40%	9%
% time between 70-180mg/dL	60%	9%
% time above 180mg/dL	35%	9%
% time above 250mg/dL	11%	5%
% time above 300mg/dL	4%	3%
Average CGM [mg/dL]	162.0	15.0

1111 This analysis will be performed using a single group one sided t-test for mean comparison for
1112 outcomes that can be assumed normally distributed and One-Sample Wilcoxon Signed Rank test
1113 for median comparison for the others, this analysis is not powered.

1114 Secondary outcomes will be reported for the entire period and for the supervised and home phases
1115 separately. Outcomes by phase will be compared to each other to assess possible loss of
1116 performances during the transition at home. For this purpose, McNemar's tests will be used to
1117 compare the supervised phase to the home phase for the primary outcome and secondary outcome
1118 # 6, 7, and 8. All other outcomes will be analyzed using repeated measure ANOVA. Significance
1119 of 0.05 will be used.

1120 This analysis is not powered.

1121 **Chapter 14: DATA COLLECTION AND MONITORING**

1122 **14.1 Case Report Forms and Device Data**

1123 The study data are collected through a combination of case report forms (electronic and paper) and
1124 electronic device data files obtained from the software and individual hardware components.
1125 These electronic device files and electronic CRFs are considered the primary source
1126 documentation.

1127 When data are directly collected in electronic case report forms, this will be considered the source
1128 data. Records will be maintained in accordance with ICH E6 and institutional regulatory
1129 requirements for the protection of confidentiality of participants.

1130 **14.2 Study Records Retention**

1131 Study documents should be retained for a minimum of 2 years after the last approval of a marketing
1132 application in an ICH region and until there are no pending or contemplated marketing applications
1133 in an ICH region or until at least 2 years have elapsed since the formal discontinuation of clinical
1134 development of the investigational product. These documents should be retained for a longer
1135 period, however, if required by local regulations. No records will be destroyed without the written
1136 consent of the sponsor, if applicable. It is the responsibility of the sponsor to inform the
1137 investigator when these documents no longer need to be retained.

1138 **14.3 Protocol Deviations**

1139 A protocol deviation is any noncompliance with the clinical trial protocol, Good Clinical Practices
1140 (GCP), or procedure requirements. The noncompliance may be either on the part of the participant,
1141 the investigator, or the study site staff. As a result of deviations, corrective actions may be
1142 developed by the site and implemented as appropriate. Major deviations will be reported to the
1143 IRB-HSR within 7 calendar days of when the study team becomes aware of the event.

1144 **Chapter 15: ETHICS/PROTECTION OF HUMAN PARTICIPANTS**

1145 **15.1 Ethical Standard**

1146 The investigator will ensure that this study is conducted in full conformity with Regulations for
1147 the Protection of Human Participants of Research codified in 45 CFR Part 46, 21 CFR Part 50, 21
1148 CFR Part 56, and/or the ICH E6.

1149 **15.2 Institutional Review Boards**

1150 The protocol, informed consent form(s), recruitment materials, and all participant materials will
1151 be submitted to the IRB for review and approval. Approval of both the protocol and the consent
1152 form must be obtained before any participant is enrolled. Any amendment to the protocol will
1153 require review and approval by the IRB before the changes are implemented to the study. All
1154 changes to the consent form will be IRB approved; a determination will be made regarding whether
1155 previously consented participants need to be re-consented.

1156 **15.3 Informed Consent Process**

1157 **15.3.1 Consent Procedures and Documentation**

1158 Informed consent is a process that is initiated prior to an individual's agreement to participate in
1159 the study and continues throughout the individual's study participation. Extensive discussion of
1160 risks and possible benefits of participation will be provided. Consent forms will be IRB approved
1161 and the participant will be asked to read and review the document. The investigator or their
1162 delegate will explain the research study to the parent/guardian(s) and answer any questions that
1163 may arise. All participants will receive a verbal explanation in terms suited to their comprehension
1164 of the purposes, procedures, and potential risks of the study and of their rights as research
1165 participants. Parent/guardian(s) will have the opportunity to carefully review the written consent
1166 form and ask questions prior to signing.

1167 The parent/guardian(s) will sign the informed consent document prior to any procedures being
1168 done specifically for the study. The parent/guardian(s) may withdraw their child's consent at any
1169 time throughout the course of the trial. A copy of the informed consent document will be given to
1170 the parent/guardian(s) for their records. The rights and welfare of the participants will be protected
1171 by emphasizing to them that the quality of their medical care will not be adversely affected if they
1172 decline to participate in this study.

1173 A child participant is considered enrolled when the informed consent form has been signed.

1174 **15.3.2 Participant and Data Confidentiality**

1175 The study monitor, representatives of the IRB or device company supplying study product may
1176 inspect all documents and records required to be maintained by the investigator, including but not
1177 limited to, medical records (office, clinic, or hospital) for the participants in this study.

UNIVERSITY OF VIRGINIA

1178 The study participant's contact information will be securely stored at the clinical site for internal
1179 use during the study. At the end of the study, all records will continue to be kept in a secure
1180 location for as long a period as dictated by local IRB and Institutional regulations.

1181 Study participant research data, which is for purposes of statistical analysis and scientific reporting,
1182 will be transmitted to and stored at the University of Virginia Center for Diabetes Technology.
1183 This will not include the participant's contact or identifying information. Rather, individual
1184 participants and their research data will be identified by a unique study identification number. The
1185 study data entry and study management systems used by research staff will be secured and
1186 password protected. At the end of the study, all study databases may be de-identified and archived
1187 at the University of Virginia Center for Diabetes Technology.

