483 team. Glycemic Treatment Guidelines to be used during the hotel admission are defined in section
484 7.1.

485 **5.2 Hotel Staffing Qualifications**

486 There will be at least one physician, advanced practice provider, registered nurse, and/or other
487 medical personnel who are specifically trained in diabetes management and trained technicians
488 supervising the Hotel Admission. Certification of their skill is supervised by the clinical site PI.
489 All medical personnel who will have direct contact with the child participants will have current
490 certification in Basic Life Support including CPR. Study personnel, trained in the use and
491 maintenance of the Tandem t:slim X2 with Control-IQ Technology, will be monitoring the system
492 during the entire trial.

493 There will be a team of at least 3 experienced study personnel in attendance during the day (7 p.m.
494 - 7 a.m.) and one study staff member during the overnight hours of 7 p.m. – 7 a.m. during the hotel
495 admission. These staff members will be proficient with devices, the study protocol and its
496 procedures, including the glycemic safety protocols.

497 Glucagon for the emergency treatment of hypoglycemia will be available on-site.

498 **5.3 Pre-Admission Check-in Visit**

499 The parent/guardian(s) will be contacted by the study team approximately 48-72 hours prior to the
500 hotel admission to verify the following information:

501 • Inquire about any changes to the child participant's health (e.g. illness, medications, etc...)

502 • Inquire about current use of the study equipment

503 • Remind parent/guardian(s) to bring all current medications for use during the study.

504 • Determine what pump profile(s) the subject uses on certain days

505 • Verify that a new CGM sensor will be placed approximately 48 hours prior to the admission
506 for proper warm up

507 • Verify with the subject that the goal CGM reading at time of arrival is less than 250 mg/dL

508 Should any concerns regarding medical history, pump information, or unforeseen issues arise, the
509 admission may be cancelled for that participant at the discretion of the investigator.

CLINICAL PROTOCOL

510 Additional phone contact(s) can occur at the study team's discretion.

511 **5.4 Admission Check-In (times are approximate)**

512 On day 1 of the admission, parent/guardian(s) and child participants will arrive to the hotel at

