603 **6.6 Post-Study Check-in Visit**

604 Approximately 48 hours after the home use of the equipment, the study team will contact the
605 parent/guardian(s) via phone/email/text to assess:

606

- 607 • adverse events, adverse device effects, and device issues
- 608 • blood glucose values <60 mg/dL and >300 mg/dL
- 609 • verify collection of ketone measurement data
- answer any questions related to device use

CLINICAL PROTOCOL

610 • unscheduled calls during the study period may be recommended for additional device
611 training or other unanticipated needs

612 **6.7 Questionnaire**

613 Parent/Guardian(s) will be asked to complete a Technology Acceptance Questionnaire (Parent
614 Version) asking them their perceptions and feeling about the technology used during the Hotel
615 Admission.

616 **Chapter 7: GLYCEMIC TREATMENT GUIDELINES**

617 **7.1 Hotel Admission Glycemic Guidelines**

618 Upon arrival, the subject will be asked to check the CGM reading and ketone concentration using
619 the study ketone meter. If CGM is <70 mg/dL or >300 mg/dL, or ketone test is >0.6 mmol/L, the
620 study physician will suggest appropriate treatment. The study team may request fingersticks as
621 needed. The study subject may continue participation in the trial once CGM is between 70-300 mg
622 /dL and ketone concentration is ≤ 0.6 mmol/L.

623 If CGM < 80 mg/dL during the day, the patient will be treated until CGM reads >80 mg/dL. If
624 CGM < 70 mg/dL during the night, hypoglycemia treatment will be provided until CGM reads $>$
625 80 mg/dL. SMBG may be performed if the MD on-call deems it necessary.

626 If CGM >300 mg/dL for more than 60 minutes, SMBG will be performed every 60 minutes. If
627 SMBG >300 mg/dL, the Glycemic Treatment Guidelines will be applied.

628 If CGM <80 mg/dL at any time, subjects will be given approximately 16 grams of fast-acting
629 rescue carbohydrates. Study team will monitor CGM rise and will consider treating again if CGM
630 <80 mg/dL after approximately 20 minutes. Hypoglycemic treatments can occur at any time per
631 study physician request.

632 Parent/guardian(s) will be asked to respond to both hypoglycemia and hyperglycemia alarms
633 during the Hotel Admission. If they do not respond to the alarms within 10 minutes, study
634 personnel will assist as per the Glycemic Treatment Guidelines.

635 Medical personnel and emergency supplies (e.g. glucagon) will be available on site.

636 **7.2 At-Home Glycemic Guidelines**

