637 **7.2.1 CGM Measurements**

638 CGM values are updated every 5 minutes and parents will be able to see it on the pump and
639 Dexcom App.

640 CGM alarms on the study team controlled Dexcom App will be set at 70 mg/dL for 30 minutes and
641 300 mg/dL for 60 minutes.

642 If CGM < 80 mg/dL during the day, the patient will be treated until CGM reads >80 mg/dL. If
643 CGM < 70 mg/dL during the night. Hypoglycemia treatment will be provided until CGM reads $>$
644 80 mg/dL. SMBG may be performed if the MD on-call deems it necessary.

645 If CGM >300 mg/dL for more than 60 minutes, SMBG will be performed every 60 minutes. If
646 SMBG >300 mg/dL, the Glycemic Treatment Guidelines will be applied.

647 A study team member will contact the family if either of the above conditions is triggered and
648 confirm treatment per provided guidelines.

649 **7.2.2 Ketone Measurements**

650 Parent/guardian(s) will be advised to test for ketones any time the CGM is above 300 mg/dL for
651 more than 2 hours.

652 If ketones are 0.6-3.0 mmol/L, the following guidelines should be followed until SMBG < 250
653 mg/dL.

- 654 • Notify MD as soon as possible
- 655 • Consider taking correction dose of insulin by syringe or pen
- 656 • Change insulin in reservoir and tubing and change pump site
- 657 • Drink sugar-free beverages
- 658 • Once BG is 100-250 mg/dL, restart pump treatment in appropriate mode. Record the
659 amount of insulin that was given when prompted

660 If ketones are >3.0 mmol/L, the following guidelines should occur:

- 661 • The participant will stop the study
- 662 • Notify MD as soon as possible
- 663 • Disconnect the STUDY insulin pump and start HOME insulin pump once instructed by
664 MD
- 665 • Take correction dose of insulin by syringe or pen
- 666 • Drink sugar-free beverages

667 **Chapter 8: REMOTE MONITORING**

668 **8.1 Hotel Admission Monitoring**

669 Parent/guardian(s) will remotely monitor the subjects in real-time using the DexCom G6 App
670 capabilities provided by Dexcom® Inc. during the Hotel Admission.

671 Staff will remotely monitor the subjects in real-time using the DexCom G6 capabilities provided
672 by Dexcom® Inc. . Notification will be set for CGM readings below 80mg/dl during the day and
673 70mg/dl at night or above 250mg/dl to alert study staff of the need treatment or SMBG
674 confirmation. In case of remote monitoring failure, CGM alarms will be activated at low=70

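### Section 7.1 gives two hotel night-time treatment limits (below 70 and below 80 mg/dL), 7.2.1 and 8.2 give two delays for the same staff home alert, and 5.4 prints the ketone trigger in the wrong direction

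*Combined protocol and SAP*

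**What the plan says.** **Hotel treatment limit.** Section 7.1 treats below 80 mg/dL by day. For the night it says "CGM < 70 mg/dL during the night, hypoglycemia treatment will be provided until CGM reads" above 80 mg/dL. Later in the same section it says "If CGM <80 mg/dL at any time, subjects will be given approximately 16 grams of fast-acting" rescue carbohydrate, with no distinction between day and night. In section 8.1 the staff notification is set at 80 mg/dL by day and "70mg/dl at night or above 250mg/dl to alert study staff of the need treatment or SMBG" confirmation. The home rule in 7.2.1 uses 80 by day, and for the night "CGM < 70 mg/dL during the night. Hypoglycemia treatment will be provided until CGM reads" above 80.

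**Meaning of night.** The treatment rules give no clock hours. Section 5.2 gives staffing hours: "There will be a team of at least 3 experienced study personnel in attendance during the day (7 p.m" and, on the next line, "7 a.m.) and one study staff member during the overnight hours of 7 p.m. – 7 a.m". Day and night thus carry the same hours.

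**Staff alert at home.** Section 7.2.1 says "CGM alarms on the study team controlled Dexcom App will be set at 70 mg/dL for 30 minutes and" "300 mg/dL for 60 minutes". Section 8.2 sets the second-tier staff alert at below 70 mg/dL for more than 15 minutes and above 300 mg/dL for more than 60 minutes. Section 6.1 sends the study team's home monitoring to 8.2. Section 4.1.1 gives families the 7.2 guidelines to use at home.

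**Ketones.** Section 5.4 lets the study physician recommend corrective action before Control-IQ starts if CGM is outside 80–300 mg/dL or ketones are at or below 0.6 mmol/L. Section 7.1 acts on ketones above 0.6, and both 7.1 and 5.10 treat values at or below 0.6 as acceptable.

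**The concern.** These are standing action thresholds in children under 6. Under 1.5.3 each of the three sites runs the trial independently, so a site that meets two rules in one section has to choose between them. Overnight the hotel may have a single staff member (5.2), who must act under these guidelines if a parent has not answered an alarm within 10 minutes (7.1). That person needs one limit.

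At home, families hold a guide that says 30 minutes while staff are directed to a section that says 15. A family could therefore expect the back-up call at a different time from the one staff work to.

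The ketone sentence in 5.4, read alone, directs attention to the wrong children.

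**Working it through.** No sample size, power or error rate is involved. The check sets the rules side by side.

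**1. Hotel, night-time CGM reading**

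| Reading (mg/dL) | 7.1 day/night rule | 7.1 round-the-clock rule | Staff notified (8.1) |
|---|---|---|---|
| below 70 | treat | treat, about 16 g | yes |
| 70–79 | no treatment called for | treat, about 16 g | no |
| 80 or above | none | none | no |

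The conflict is confined to a band of 80 − 70 = 10 mg/dL, at night only; by day both rules say 80. Three statements give 70 at night (the 7.1 day/night rule, 8.1 and 7.2.1) and one gives 80. The round-the-clock sentence is the outlier.

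**2. What night should mean.** The only overnight hours are the staffing hours in 5.2: 7 p.m. to 7 a.m., or 12 h. Section 5.6 puts dinner at about 6–7 p.m. and encourages bedtime by 9 p.m.; 9 p.m. to 7 a.m. is 10 h. Using the staffing hours would lower the limit from 80 to 70 for 12 − 10 = 2 h each evening, while children may still be awake after a dinner bolus. Over two hotel nights that is 4 h per child. The staffing hours are therefore the wrong definition for treatment.

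**3. Staff low alert at home**

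| | 7.2.1 | 8.2 |
|---|---|---|
| Who and where | study team, home | study staff, home |
| Low limit | 70 mg/dL | below 70 mg/dL |
| Low delay | 30 min | more than 15 min |
| High limit and delay | 300 mg/dL, 60 min | above 300 mg/dL, more than 60 min |

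Everything except the low delay matches, so this is one alert with two delays. The difference is 30 − 15 = 15 min, a factor of 30/15 = 2. At one CGM value every 5 minutes (7.2.1) that is 6 readings against 3. The cross-reference in 6.1 makes 15 the governing value.

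**4. Ketones.** As printed, 5.4 flags 0.3 mmol/L and not 2.0; 7.1 flags 2.0 and not 0.3. In 5.4 the negation belongs to the CGM clause, and the ketone clause has its own verb, so the printed direction is reversed. A symbol misread from the PDF cannot be fully excluded and should be checked against the source file.

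**5. What cannot be computed.** Suppose lows are spread evenly over time and the analysis window is 48 + 72 = 120 h (an assumption; 13.2.1 states no window). Two hotel nights are 2 × 10 = 20 h to 2 × 12 = 24 h.

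- At the 6% limit in 13.2.1: 0.06 × 20/120 = 1.0 point to 0.06 × 24/120 = 1.2 points.
- At the 2.8% closed-loop mean in Table 1: 0.028 × 20/120 = 0.47 to 0.028 × 24/120 = 0.56 points.

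These figures count the time below 70 that falls on hotel nights. They do not say how much of it either treatment rule would remove, so they do not size the conflict.

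**The case against.** **The protocol resolves much of this itself.** Section 6.1 settles the alert delay in favour of 8.2, and staff are in any case a second tier behind a parent alert at 70 mg/dL with no stated delay. It is also not certain that the 30 minutes governs the staff call. The sentence in 7.2.1 about contacting the family follows the treatment rules more closely than the alarm setting. All of this stands. What remains is that families are given the section with the stray value.

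**The two sentences in 7.1 can be followed together.** The night rule forbids nothing at 70–79 mg/dL, 7.1 allows treatment whenever the study physician asks for it, and treating below 80 satisfies both sentences. That is literally true. But the night limit of 70 then has no function, and 8.1 would not notify staff of the readings they are meant to treat. Physician discretion does not say which limit is the standing rule. It is fair that practical exposure is narrow for the same 8.1 reason, and that divergence between sites is a possibility rather than a known fact.

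**Section 5.4 does little harm.** It is discretionary and refers to 7.1, which has the right direction and applies on arrival. This stands, so the ketone item is a wording correction.

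**A stronger reading is tempting.** A reader might infer that the 7.1 conflict biases the primary outcome, or that it spoils the supervised-versus-home comparison in 13.2.4. The documents do not support either. More rescue carbohydrate lowers time below 70 but can raise time above 180, and the primary outcome needs both, so even the direction is unknown. The two phases already differ by design: provided meals, group activities, staff on site, and tighter daytime staff notification in the hotel. Section 13.2.4 states that the comparison is not powered. Making 7.1 consistent would not make the phases comparable.

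**Conclusion.** The inconsistencies are real and sit in current operative text. For a hotel night reading of 70–79 mg/dL the standing instruction is contradictory, and the rest of the protocol points to 70. The staff home low delay is stated as both 30 and 15 minutes, with 15 governing through 6.1. The ketone sign in 5.4 is reversed, with limited harm, subject to checking the symbol in the source PDF.

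The reason to act is that children under 6 at three independently run sites should be treated under one rule, and that correcting it is trivial. No measurable effect on the primary outcome, on the count of carbohydrate treatments or on the phase comparison is claimed. The conclusion rests on 7.2.1 and 8.2 describing the same alert, which their matching limits and high-alert settings support.

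**What to change.** 1. **Section 7.1:** replace the round-the-clock 80 mg/dL trigger for the 16 g treatment with below 80 mg/dL during the day or below 70 mg/dL at night. Define night as the child's sleep period, for example bedtime (about 9 p.m.) to 7 a.m., and not the 7 p.m.–7 a.m. staffing hours. Correct the daytime hours in 5.2. If 80 throughout is what is wanted, raise the 7.1 night rule and the 8.1 night notification to 80 instead, and say whether the home night rule in 7.2.1 changes too.
2. **Section 7.2.1:** change 30 minutes to 15 to match 8.2.
3. **Section 5.4:** change the ketone trigger to above 0.6 mmol/L.

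The cost is a few words by amendment or clarification letter, with no change to recruitment or analysis. Item 2 would mean somewhat more staff calls if any site had been using 30 minutes.
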